9.2. Infusion Reactions

Since SHR-1210 is a fully humanized monoclonal antibody, the possibility of infusion reactions is small, and no pre-dose prophylactics are required. If an infusion reaction occurs, the infusion should be slowed or interrupted according to the situation, and a supportive treatment should be given. In addition, prophylactics should be given before further administration. Signs and symptoms of acute infusion reactions (including cytokine release syndrome, angioedema, anaphylactic shock, and allergic reaction, refer to the terms and criteria in NCI CTCAE v4.03) usually occur during or after the infusion and disappear within 24 h after infusion. The signs and symptoms include: allergic reaction/hypersensitivity reaction (including drug-induced fever), coughing, chills, rigor, dizziness, headache, fatigue (weakness, somnolence), rash/peeling skin, pruritus/itching, arthralgia, myalgia, hypotension/hypertension, nausea, vomiting, diaphoresis, tachycardia, cancer pain, urticaria, dyspnea (shortness of breath), or bronchospasms. All Grade 3 or 4 infusion reactions should be reported to the sponsor within 24 h. An infusion reaction meeting the criteria of an SAE should be reported as an SAE.

Management of allergic reactions should be based on the medical practice and guidelines of the study site. The treatment recommendations for infusion reactions are as follows for reference.

Table 4. Treatment recommendations for infusion reactions

CTCAE Grade	Clinical Symptoms	Clinical Management	SHR-1210 Treatment
Grade 1 (Mild)	Mild and transient reactions;	Bedside observation and close monitoring until recovery. (Pre-dose prophylactics are recommended for subsequent administrations: 50 mg of diphenhydramine or equivalent, and/or 325-1000 mg of acetaminophen, at least 30 min before the administration of SHR-1210)	Continuation
Grade 2 (Moderate)	Moderate reactions requiring treatment or interruption; rapidly resolve after symptomatic treatment (such as antihistamines, non-steroidal antiphlogistics, anesthetics, bronchodilators, intravenous fluids, etc.)	Intravenous administration of normal saline: 50 mg of diphenhydramine IV or equivalent and/or 325-1000 mg of acetaminophen; Bedside observation and close monitoring until recovery. Corticosteroids or bronchodilators can be considered based on clinical needs; The amount of investigational drug infused should be recorded in the original medical record; Pre-dose prophylactics are recommended for subsequent administrations: 50 mg of diphenhydramine or equivalent and/or 325-1000 mg of acetaminophen can be given at least 30 min before the administration of SHR-1210. Use corticosteroids (equivalent to 25 mg of hydrocortisone) when necessary.	Interruption. Re-administer at 50% of the initial rate after symptoms resolve. If no reaction occurs within 30 minutes, restore the original infusion rate (100%). Closely monitor. If the symptoms recur, the current SHR-1210 should be discontinued.
Grade \geq 3 (Severe)	Grade 3: Severe reaction without rapid recovery upon treatment and/or interruption; or symptoms recur after alleviation; or the subject develops sequelae that requires hospitalization. Grade 4 (Life-threatening)	Immediately discontinue SHR-1210; Intravenous administer normal saline. 
 Bronchodilators are recommended: subcutaneous injection of 0.2-1 mg of 1:1000 adrenaline solution or slow intravenous injection of 0.1-0.25 mg of 1:10000 adrenaline solution, and/or 50 mg of diphenhydramine plus 100 mg methylprednisolone or equivalent by intravenous injection if necessary; Based on the study site's guidelines for treating allergic reactions; Bedside observation and close monitoring until recovery.	Permanent discontinuation.

9.3. Symptomatic Treatment for Apatinib-Related Adverse Reactions

1) Hand-and-foot syndrome (HFS)

HFS is a skin toxicity with palmar-plantar dysaesthesia or acral erythema and manifests especially in areas under pressure or force. It may occur in patients with tumor during chemotherapy or molecular targeted therapy. HFSR is characterized by numbness, dysesthesia, paraesthesia, tingling, no pain or pain, skin swelling, or erythema, desquamation, chapping, scleroma-like blisters, and severe pain.

HFS grading:

Grade 1: numbness/dysesthesia/paraesthesia, painless swelling or erythema of the hands and/or feet and/or discomforts that does not affect normal activities.

Grade 2: painful erythema and swelling of the hands and/or feet and/or discomforts affecting patients' activities of daily living.

Grade 3: wet desquamation, ulcers, blisters, or severe pain of hands and/or feet and/or severe discomforts that causes the patients to be unable to work or perform activities of daily living. Intense pain and loss of skin function, relatively rare.

Symptomatic treatment and management of HFS:

Some necessary symptomatic and supportive treatments must be taken, including: strengthen skin care, keep skin clean, and avoid secondary infections; avoid pressure or friction; use moisturizers or lubricants, topically use lotions or lubricants containing urea and corticosteroids; topically use antifungal or antibiotic treatment if necessary.

Note: If a HFS of Grade 3 or above occurs for more than 3 consecutive times with an aggravating trend, the subject should discontinue the study treatment and withdraw from the clinical study.

2) Hypertension

Patients should be strictly screened according to blood pressure requirements in the inclusion and exclusion criteria prior to enrollment. Patients with hypertension can control the blood pressure by adjusting the dose of or adding new antihypertensive drugs before administering the investigational drug. The blood pressure must be under 140/90 mmHg (average of 2 blood pressure measurements taken at least 24 h apart) before randomization.

Monitoring and handling of such hypertension: Blood pressure should be monitored at least 3 times a week during the first 2 cycles of the targeted pharmacological treatment.

Since anti-VEGF/VEGFR targeted drugs can decrease the synthesis of NO and ultimately activate the renin-angiotensin-aldosterone system to cause hypertension, angiotensin converting enzyme (ACE) inhibitors (such as captopril, enalapril, benazepril, and cilazapril) are preferred for antihypertensive therapy. For some patients who are allergic or intolerant to ACE inhibitors, angiotensin II receptor blockers (ARB, such as losartan, valsartan, irbesartan and telmisartan) can be used for treatment. In addition to lowering the blood pressure, ARB is also beneficial for alleviating proteinuria. ACE inhibitors can be used in patients with chronic kidney diseases, proteinuria and metabolic syndrome; dihydropyridine calcium ion antagonists are suitable for elderly patients.

When subjects develop hypertension or aggravated hypertension during drug administration, the following measures should be used: 1) adjust the study drugs according to the protocol (see table below); 2) start the administration of antihypertensive drugs or adjust the dose of antihypertensive drugs.

Antihypertensive drugs recommended for the trial: 1) angiotensin converting enzyme inhibitor (ACEI); 2) angiotensin II receptor blocker (ARB); 3) dihydropyridine calcium channel blocker; 4) β -receptor blocker.

Diuretic antihypertensive drugs are not recommended. Antihypertensive drugs with an inhibitory effect on CYP3A4, such as nifedipine, diltiazem and verapamil, are prohibited during the administration period of the investigational drug. For those with hypertensive crisis, the application of apatinib should be terminated.

3) Hemorrhage

Symptomatic treatment should be actively given for gastrointestinal hemorrhage, including fecal occult blood (++) and above, hematemesis or bloody stool. Patients with upper gastrointestinal hemorrhage should be fasted and given acid suppression, gastric mucosal protection, hemostasis (transamin, reptilase, etc.), as well as octreotide if necessary; patients with lower gastrointestinal hemorrhage should be given hemostasis, blood transfusion and supportive care, etc.; for those whose bleeding cannot be controlled, assistance from the surgery department should be requested immediately.

Patients with hemoptysis should be given hemostasis, blood transfusion and supportive care, etc.; for those whose bleeding cannot be controlled, assistance from the surgery department should be requested.

Note: Patients with cerebral hemorrhage, Grade II or higher pulmonary hemorrhage, and Grade III or higher hemorrhage should stop the study treatment immediately, undergo symptomatic treatment, terminate apatinib administration, and discontinue SHR-1210 administration. Consider whether to resume SHR-1210 as appropriate after symptoms resolve or disappear.

4) Proteinuria

All subjects should be closely monitored for proteinuria throughout the entire treatment period, especially for those with a history of hypertension. For those with a urine protein result of ++ to +++ in 2 consecutive tests, a 24-h urine protein assay is required. For those with urine protein of ++++ and above, a 24-h urine protein assay is required.

Note: In case of nephrotic syndrome, the subject should discontinue the treatment permanently and withdraw from this clinical study.

5) Thrombosis

If any arterial thrombosis (such as cerebral ischemia, stroke, angina pectoris, myocardial infarction, etc.) occurs, the subject should discontinue the treatment immediately and withdraw from the study. In case of any symptomatic IV venous thrombosis, the subject should discontinue the treatment and withdraw from the study.

Once the symptoms are observed, symptomatic treatment, surgery, or anticoagulants shall be immediately given.

6) Fatigue and weakness

Fatigue and weakness are common tumor-related clinical symptoms, the cause of which might be electrolyte disturbance, abnormal liver function, abnormal cardiac function, etc. Also, fatigue and weakness are common adverse reactions of targeted anti-angiogenic drugs, such as sunitinib, pazopanib, and sorafenib. Clinical reports show that targeted anti-angiogenic drugs may increase the incidence of fatigue and weakness through hypothyroidism.

In previously completed clinical trial of apatinib, subjects in the test group showed a higher incidence of fatigue and weakness than those in the control group, and the mechanism behind the increased incidence of fatigue and weakness caused by apatinib is yet unidentified.

Therefore, close attention should be paid when a patient shows and reports Grade II or higher fatigue and weakness. In the case of Grade III or higher fatigue and weakness, the patient should be admitted to the hospital immediately for detailed examinations to exclude possible reasons such as electrolyte disturbance, abnormal liver function, cardiac dysfunction (ECG, echocardiography), and abnormal hormone levels (adrenal hormones, thyroid hormones). A symptomatic treatment should be given and the dose should be interrupted or modified according to the principle of dose modification.

7) Abdominal pain

Abdominal pain is not uncommon in the treatment with apatinib, which are mostly a concomitant symptom of tumor. Also, gastrointestinal perforation occasionally occurs in clinical trials of apatinib and other anti-angiogenic drugs. For subjects with abdominal pain, the investigator should be cautious of potential gastrointestinal perforation. Upon the observation of gastrointestinal perforation, the drug should be discontinued immediately, and the subject should withdraw from the trial and be given an active symptomatic treatment.

8) Interstitial pulmonary fibrosis

The clinical physicians should fully understand the conditions of subjects and be familiar with the drugs that may lead to pulmonary toxicity. The clinical symptoms and changes in chest X-ray or CT are closely monitored. Once cough, chest tightness, labored breathing, dyspnea, and hemoptysis of unknown causes, the drug should be discontinued as soon as other causes (such as infection and heart failure) are ruled out. Alveolar lavage fluid analysis and surgical lung biopsy are important means to diagnose interstitial lung disease. Currently, no therapy yields a satisfactory result against pulmonary fibrosis, and correction of hypoxemia and timely administration of corticosteroids are recommended following "Guidelines for Diagnosis and Treatment of Idiopathic Pulmonary (Interstitial) Fibrosis" issued by the Chinese Medical Association Respiratory Diseases Branch.

Note: Consult specialists when necessary.

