- [5] Urinalysis: Urine protein, urine glucose, urine occult blood, urine red blood cells, and urine white blood cells. If 2 consecutive semi-quantitative tests show proteins of 2+, or a semi-quantitative test shows proteins > 2+, a quantitative 24-h urine protein test is required. Performed within 7 days before the enrollment, on Day 15 of Cycle 1, Day 1 and Day 15 of subsequent cycles, at the end of study, and 30 days after the treatment.
- [6] Routine stool test: Patients with positive fecal occult blood must be retested. If fecal occult blood is confirmed, then a gastroscopy is performed. If fecal occult blood occurs during the course of the study, the subject should undergo a gastroscopy if deemed necessary by the investigator. Performed within 7 days before enrollment, on Day 15 of Cycle 1 and Day 1 of subsequent cycles, and at the end of study.
- [7] Coagulation function: INR, APTT, PT, FIB; Performed within 7 days before enrollment, on Day 15 of Cycle 1 and Day 1 of subsequent cycles, and at the end of study.
- [8] Thyroid function test: Including serum FT3, FT4 and TSH. Performed within 21 days before dosing, on Day 1 of Cycle 2, once every 3 cycles thereafter, and at the end of the study.
- [9] Hepatitis B and C test: Subjects with abnormal hepatitis B markers should undergo quantitative tests of HBV DNA and HBsAg. Subjects with positive anti-hepatitis C virus (HCV) antibodies must be tested for HCV titer (HCV RNA). Subjects with abnormal baseline HBsAg must be tested for HBV DNA and HBsAg levels on D1 \pm 7 d every 2nd cycle and at the end of study.

- [10] Pregnancy test: The urine pregnancy test shall be performed 72 h before the first dose in women of childbearing potential. If positive, a serum pregnancy test shall be performed. If necessary, a re-test can be performed for confirmation. By considering the subjects' condition, the test can be performed as needed and at the end of the study.
- [11] Myocardial zymography: performed within 7 days prior to enrollment, when deemed necessary by the investigator, and at the end of treatment/upon withdrawal.
- [12] Pituitary adrenal axis test: Including ACTH, cortisol, and follicle stimulating hormone, which shall be performed within 21 days before dosing during the screening period.

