5.1.5. Administration

SHR-1210 is an intravenous injection drug that must be administered by qualified or experienced trial staff in the outpatient department or ward of the study center. Administration is not permitted outside the study center.

Subjects must complete all clinically required examinations except for tumor assessments within 72 hours prior to each dose, to determine whether continuing the medication is appropriate.

SHR-1210 is infused intravenously over a period of 30 minutes (no less than 20 minutes and no more than 60 minutes, including the flushing of the infusion line). Do not administer by intravenous bolus or rapid bolus injection.

The intravenous drip infusions are performed through a medical infusion bag using an infusion set with an in-line filter (0.2 µM).

Do not use this infusion line to administer other drugs before and after infusion.

Apatinib mesylate is an oral tablet. The investigator prescribes the medicine and the subjects shall take the medicine orally after meal at home. Refer to the dosing regimen for details.

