6.2. Trial Period

D1 of Cycle 1 [Vital signs] [Physical examinations and weight measurement] [Intravenous drip of SHR-1210] [Dispensation of apatinib] [Administration of apatinib]

Within 24 h after the first dose of SHR-1210, the subjects should be closely monitored for acute allergic reactions. If an acute allergic reaction occurs, it should be treated according to the medical practice of the hospital and relevant guidelines.

In order to improve the compliance of the subjects and ensure that apatinib is taken after breakfast every day, only SHR-1210 is administered on D1 of Cycle 1 while the oral administration of apatinib is started on D2 after breakfast, and will be continuously given in cycles of 4 weeks.

D15 of Cycle 1 [Hematology] [Blood biochemistry] [Urinalysis] [Stool routine] [Coagulation function] [Vital signs] [Physical examination and weight measurement] [ECG] [Intravenous drip of SHR-1210] [Adverse events] [Concomitant medication]

D1 of subsequent cycles [Routine blood test] [Biochemistry] [Routine urinalysis] [Routine stool test] [Coagulation] [Vital signs] [Physical examinations and weight measurement] [ECOG PS] [ECG] [SHR-1210 IV drip infusion] [Adverse events] [Concomitant medication]
[Retrieval/dispensing of apatinib]

D15 of subsequent cycles: [Hematology] [Blood biochemistry] [Urinalysis] [Vital signs] [Physical examination and weight measurement] [Intravenous drip of SHR-1210] [Adverse events] [Concomitant medication]

A window period of ± 3 d is set and the intravenous administration of SHR-1210 should be carried out after the evaluation of examinations and tests specified in the flowchart is completed.

[Imaging evaluation] During the treatment period, the imaging examination should be performed under the same conditions as those of the baseline examination (layer thickness of the scan, use of contrast agent, etc.), and the baseline lesions should be checked every 2 cycles during the first 12 treatment cycles (bone scan will be performed if bone progression is suspected or CR is confirmed), and then once every 3 cycles thereafter. Appropriate examination may also be performed if new lesions are suspected. The first documentation of PR/CR in a subject must be verified 4 weeks \pm 7 days later. A radiological confirmation is required 4-6 weeks after the first documentation of disease progression as per RECIST 1.1 (except those with rapid progression or significant clinical progression);

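### Protocol 9.3 and 6.1 state weaker triggers for the 24-h urine protein test than schedule note [5], and neither 6.1 nor note [5] explicitly orders it after a single screening ++

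*Protocol*

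**What the plan says.** Three places in the Protocol set a trigger for the 24-h urine protein test.

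- **9.3, item 4 (Proteinuria).** It opens with "All subjects should be closely monitored for proteinuria throughout the entire treatment period". It then gives a two-test rule, "For those with a urine protein result of ++ to +++ in 2 consecutive tests, a 24-h urine protein assay is required", and a single-result rule, "For those with urine protein of ++++ and above, a 24-h urine protein assay is required".
- **Procedures of the Trial, note [5].** The test is required after two consecutive results of 2+, "or a semi-quantitative test shows proteins > 2+, a quantitative 24-h urine protein test is required". The timing is "Performed within 7 days before the enrollment, on Day 15 of Cycle 1, Day 1 and Day 15 of subsequent cycles", with further tests at the end of study and 30 days after treatment.
- **6.1 Screening Period, routine urinalysis.** Only the branch with two consecutive 2+ results appears. The single-result branch of note [5] is absent.

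Two places use the 24-h value. In 5.3, Table 1 holds apatinib for proteinuria at Grade 3, graded on the 24-h quantification. In 4.2, exclusion 14 combines a routine urinalysis of ++ or more with a confirmed 24-h value of 1.0 g or more. Section 6.1 ends by requiring that all eligibility criteria be verified again before inclusion.

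**The concern.** The dipstick decides who gets the 24-h test. The 24-h value then decides whether Table 1 requires an apatinib hold and, at screening, whether exclusion 14 applies. If the trigger depends on the page a site reads, so does the timing of that decision. Section 9.3 is where a clinician managing an apatinib reaction would naturally look, and the trial runs at about 25 sites.

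On treatment, the risk is that a patient with a single +++ continues apatinib while a Grade 3 value goes unmeasured. At screening, the risk is that a patient with a single ++ is enrolled without the 24-h value that exclusion 14 depends on.

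**Working it through.** The plan states no figure on this point, so there is none to reproduce. The check sets the three rules side by side and then counts days in the schedule.

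**Does the text itself require a 24-h test?**

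| Result | Note [5] | 9.3 (on treatment) | 6.1 (screening) |
|---|---|---|---|
| single ++ | no | no | no |
| single +++ | yes | no | no |
| single ++++ | yes | yes | no |
| two consecutive ++ | yes | yes | yes |

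On treatment, note [5] and 9.3 differ in one row only, the single +++. Section 9.3 is not silent on +++, because it places that result on the two-test path.

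At screening, exclusion 14 needs the 24-h value for ++, +++ and ++++. Note [5] covers its own screening urinalysis, so it orders the test at +++ and ++++. That leaves a single result of exactly ++ without an explicit order in either text.

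**On-treatment interval.** After Cycle 1 Day 15, urinalysis falls on Days 1 and 15 of each 28-day cycle, so scheduled tests are 14 days apart. Each visit has a window of ±3 days. The shortest gap is 14 − 3 − 3 = 8 days and the longest is 14 + 3 + 3 = 20 days. This is the wait to the first scheduled test that could complete 9.3's pair. If that result falls below ++, 9.3 does not require the test then either.

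**Screening count.** One urinalysis is scheduled before dosing. Section 6.2 lists none on the first treatment day: "D1 of Cycle 1 [Vital signs] [Physical examinations and weight measurement] [Intravenous drip of SHR-1210] [Dispensation of apatinib" and apatinib administration are the listed items. The next scheduled test is Cycle 1 Day 15 ± 3 days, that is, Days 12 to 18. One SHR-1210 infusion (Day 1) precedes it. Section 6.2 also says "only SHR-1210 is administered on D1 of Cycle 1 while the oral administration of apatinib is started on D2 after breakfast", so the apatinib doses taken before that test are:

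- test on Day 15: Days 2 to 14, 14 − 2 + 1 = 13 doses;
- test on Day 12: Days 2 to 11, 11 − 2 + 1 = 10 doses;
- test on Day 18: Days 2 to 17, 17 − 2 + 1 = 16 doses.

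These counts apply only to a patient who starts treatment with an unresolved ++ and no unscheduled repeat.

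**The case against.** **On treatment, the rules do not collide.** Note [5] belongs to the schedule, and the opening of section 6 requires examinations to follow that schedule. Section 6.2 also gives SHR-1210 only after the flowchart tests have been evaluated. Section 9.3 neither claims to replace the schedule nor forbids earlier testing, and it asks for close monitoring. Following note [5] satisfies both texts. This stands: a reader might infer that sites face contradictory instructions, but the stricter rule gives a determinate answer. What remains is that 9.3 writes a different threshold for the same result and does not refer back to note [5].

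**At screening, a reader might infer that 6.1's trigger can never be met.** The documents do not support that. A rule about two consecutive tests presupposes a repeat, nothing limits the 7-day window to one urinalysis, and SAP 5.5.3 foresees unplanned tests. Scheduled tests alone cannot meet the trigger, but an unscheduled repeat is not barred.

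**A reader might also infer that the plan lets a ++ patient in without a 24-h value.** That too goes beyond the text. Exclusion 14 calls for 24-h confirmation, and the final check in 6.1 requires each criterion to be verified, so the need is implied. What is missing is an explicit order. The stool item next to it in 6.1 does state a retest, and the urine item does not.

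**The general pre-dose check in 5.1.5** ("Subjects must complete all clinically required examinations except for tumor assessments within 72 hours prior to each dose") allows room for an early repeat but names no urine protein threshold, so it does not settle the trigger.

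**Investigator discretion** under 5.3 permits an apatinib interruption without a Grade 3 value. This stands, and it limits the consequence further.

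**Conclusion.** The point holds as a wording inconsistency that bears on a safety action and an eligibility check. On treatment it concerns one result, a single +++. At screening, 6.1 omits note [5]'s single-result clause, and the gap that remains once note [5] is applied is a single result of exactly ++.

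The 8 to 20 day interval and the 10 to 16 apatinib doses are conditional worst-case figures and should not be read as expected effects. A delayed hold requires all of the following: a site working from 9.3 without note [5], no early repeat, a 24-h value already at Grade 3, and no discretionary interruption. Below Grade 3, Table 1's proteinuria row requires no hold under either rule. The dose count requires a site to skip both a repeat and the implied eligibility confirmation.

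The documents do not say how often a +++ quantifies as Grade 3 or how often a single ++ occurs at screening, so no expected excess exposure can be given. The ORR analysis is not affected. The change is worth making because it is cheap and removes an avoidable difference between sites.

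**What to change.** - **9.3, item 4:** replace the two trigger sentences with note [5]'s rule, so that the 24-h test is required after two consecutive results of 2+ or any single result above 2+.
- **6.1 and note [5]:** state that at screening any dipstick of ++ or more requires a 24-h urine protein result before enrolment, and that the subject is excluded if it is 1.0 g or more. In 6.1 this replaces the two-test sentence.

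The cost is wording in three places and a few more 24-h collections, a test the Protocol already uses. At screening the collection must fit within the 7 days before the first dose. Protocol section 17 anticipated the last enrolment in December 2018 and version 3.0 is dated 29 May 2019, so the screening edit may come too late for patients already enrolled. The on-treatment edit applies for as long as anyone remains on apatinib.
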